10.2 General aspects

Descriptive statistics will be based on means (+/- standard deviation) or medians [interquartile range] depending on the distribution of quantitative variables. Qualitative variables will be described in terms of numbers and percentages. Univariate comparisons will use the usual statistical tests after verification of the distribution of the variables (Chi2 or Fisher's test, t-test, anova or their non-parametric equivalents Wilcoxon and Kruskal-Wallis tests). Paired sample tests will be used if necessary.

Tests will be performed at the 5% significance level. The 95% confidence intervals will be provided for each estimate.

The calculations will be done using SPSS v21 IBM and R software (version 3.6.1, <http://www.R-project.org>).

10.3 Morbidity and mortality criteria

10.3.1 Length of hospitalization

The length of stay is defined as the number of days of presence in the inclusion service, from the patient's admission to the final discharge. Temporary transfers to another hospital department for an examination or an intervention are not considered discharges.

A special statistical treatment (**described in section 11.4**) will be carried out on the length of hospital stay, given the impact of death on the length of stay.

10.3.2 Mortality

Number of deaths out of the total number of patients included. A specific statistical treatment (**described in section 11.4**) will be performed on the mortality rate.

10.3.3 Katz Activities Daily Living (ADL) Score

The Katz ADL score ([Appendix 1](#)) is completed within 48 hours prior to (scheduled) hospital discharge by the patient's caregiver or nurse. The total score is out of 6. A score of less than 3 indicates major dependence, a score of 0 indicates total dependence.

The Katz ADL score will be treated as a discrete numerical variable.

10.4 Analysis of the main objective

Inter- and intra-examiner reliability will be assessed by calculating intra-class correlation coefficients.

Validity will be assessed by calculating the areas under the ROC curve (Receiver Operating Characteristics) and calculating sensitivities, specificities, positive and negative predictive values.

The reference test for the diagnosis of impaired muscle function is bioelectrical impedance. The cut-off values used for the diagnosis of impaired muscle function are those recommended by GLIM (1): Appendicular Skeletal Muscle Index (ASMI) < 7 kg/M² in men and < 5.7 kg/m² in women.

10.5 Secondary objectives

10.5.1 Correlation of muscle ultrasound with standard measures of muscle function

Measures of association between quantitative variables will be performed using Pearson's or Spearman's correlation coefficients depending on the distribution of the data. Measures of association between qualitative variables will be performed using the Chi-square or Fisher test depending on the distribution of the data.

The agreement between quantitative variables will be evaluated using the Bland-Altman method and that between qualitative variables using the Kappa coefficient.

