1.4 Assessment of muscle function

Physical therapists and EAPAs use different tools to assess different aspects of muscle function, such as strength or walking speed in more functional tests.

Isometric grip strength is strongly correlated with lower extremity muscle strength, and is a pejorative marker of mobility in weakness (7). It has been

observed a linear relationship between grip strength and patient disability as measured by the Katz independence scale (11). In addition, grip strength has been shown to be a good predictor of the patient's clinical condition (12). The measurement of grip strength, using a dedicated dynamometer, also has the advantage of being simple and reproducible (13) and has reference values adjusted for sex and BMI (14).

Gait speed is another indicator used to assess muscle function. It is associated with lower limb strength and is a predictor of disability and mobility limitation (7). Usual walking speed is most often measured over a distance of 4 or 6 m and has reference values adjusted for sex and height (12).

Dietitians also participate in the evaluation of muscle function by measuring body composition in terms of lean and fat mass. They perform bioelectrical impedanceometry, which allows estimation of body fat and lean mass volumes by measuring the resistance of biological tissues to a low-intensity, high-frequency sinusoidal electric current through electrodes (7). This measurement method is simple to use, inexpensive, reproducible and feasible in bedridden patients (7). It also correlates very well with MRI and reference values are obtained in various adult populations (15,16).

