5.1 Inclusion criteria

Patients with the following criteria will be included:

- Admitted in short stay and follow-up care and rehabilitation of diabetology-obesity, pneumology, oncology and gastro-nutrition;
- Age between 18 and 70 years at inclusion;
- Affiliation with a social security system or beneficiary of such a system ;
- Oral, free, informed and express consent of the patient or his/her family member.

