9.1.2 Sampling of the population

A potential of 94 patients per month eligible for this study are admitted in short stay and follow-up care and rehabilitation of diabetes-obesity, pneumology, oncology and gastro-nutrition. We anticipate a maximum inclusion of 6 patients per month for logistical reasons.

In order to obtain a representative sample of this patient population in the study, we will sample the patient population upon admission, if he/she meets the eligibility criteria and before the patient is informed and consented. The patient will be randomly assigned to either the eligible or ineligible group. Patients in the ineligible group will not be included in the study, but the number of these patients will be collected.

Patients will be sampled via a centralized random drawing system available via the internet, according to a pre-established list. This list will be programmed in advance by the study statistician. The sampling will be stratified on the care service, and unbalanced using random blocks in order to obtain a number of eligible patients of 10 per month (in order to take into account possible refusals of participation). Only the hospital's research coordinator will know the sampling list.

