9.2 Inclusion visit

The inclusion visit will take place within 48 hours of the patient's or family member's consent to participate in the study. The following data will be collected:

- Age, weight, height, BMI, gender (male/female);
- Hospitalization Service;
- Reason for hospitalization;
- Background;
- Reduced food intake or absorption;
- Inflammatory situation;
- Biological markers (albumin, pre-albumin, CRP) if applicable;
- Nutritional data (weight evolution over the last months, theoretical needs, ingestas) ;
- Mini-Nutritional Assessment Short-Form (MNA-SF);
- Autonomy Score (Katz ADL);
- Ultrasound measurements;
- Bioelectrical impedance data;
- Grip force (Handgrip);
- Walking speed.

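### The ultrasound correlations in section 10.5.1 take no account of sex, so for handgrip and impedance part of the coefficient may reflect the difference between men and women

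*Combined protocol and SAP*

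**What the plan says.** The first secondary objective (section 3.2) is the correlation of muscle ultrasound with standard measures of muscle function. Section 4.2 names these as impedance, handgrip and walking speed. For quantitative variables, section 10.5.1 gives the method in one sentence: "Measures of association between quantitative variables will be performed using Pearson's or Spearman's correlation coefficients depending on the distribution of the data". It adds Bland-Altman agreement, but names no covariate, stratum or partial correlation.

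Nothing elsewhere in section 10 fills the gap. Section 10.2 says "Univariate comparisons will use the usual statistical tests after verification of the distribution of the variables" and "Tests will be performed at the 5% significance level", with 95% confidence intervals for each estimate. The plan never says outright that the sexes are pooled, but one coefficient over all patients is its plain reading.

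The cohort is not restricted by sex. The relevant inclusion criterion in section 5.1 is "Age between 18 and 70 years at inclusion", and section 9.1.2 says only that "The sampling will be stratified on the care service". Sex, age and height are all recorded at the inclusion visit (section 9.2).

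The protocol itself treats the three comparators as depending on sex. In section 1.4, grip strength "has reference values adjusted for sex and BMI" and usual walking speed "has reference values adjusted for sex and height". In sections 8.2 and 10.4 the impedance cut-off is 7 kg/m² for men and 5.7 kg/m² for women. Section 4.1 defines the ultrasound measure as rectus femoris thickness and states no indexing to sex or body size.

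**The concern.** When two measurements both differ between men and women in the same direction, mixing the sexes produces a positive correlation even if the measurements are unrelated within each sex. If they are related within sex, mixing usually makes the relation look stronger. Switching from Pearson to Spearman does not remove this.

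The clinician at the bedside already knows the patient's sex. The useful question is whether ultrasound tracks strength or muscle mass beyond that, and an unadjusted coefficient cannot answer it. What is at stake is how the first secondary objective is read: a moderate correlation could be taken as evidence about muscle when part of it is evidence about sex.

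**Working it through.** **The plan's own figure.** Section 10.5.1 states no expected correlation, power or sample size. The only n available is 118, from the reproducibility calculation in section 10.1 (ρ1 = 0.80, ρ0 = 0.70, k = 2, α = 0.05, power 80%). With θ = ρ/(1 − ρ), θ0 = 2.333 and θ1 = 4. Then C0 = (1 + 2 × 2.333)/(1 + 2 × 4) = 0.6296 and (ln C0)² = 0.2140. With one-sided α, N = 1 + 2 × (1.645 + 0.842)² × 2/(0.2140 × 1) = 116.6, so 117. That agrees closely with 118, which is used below.

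**Formula.** Let p be the share of men and q = 1 − p. Let dx and dy be the sex differences in ultrasound thickness and in the comparator, in within-sex SD units, and let r_w be the correlation within each sex. Then

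r_pooled = (r_w + pq·dx·dy) / √[(1 + pq·dx²)(1 + pq·dy²)].

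**Inputs.** The documents give no sex difference in thickness, no SDs and no expected sex mix. The values of dx, dy and p are therefore assumptions, shown as a range.

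**Results with equal sexes (pq = 0.25).**

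| dx, dy | pq·dx·dy | Denominator | r_w = 0 | r_w = 0.30 | r_w = 0.50 |
|---|---|---|---|---|---|
| 0.5, 1 | 0.125 | √(1.0625 × 1.25) = 1.152 | 0.11 | 0.37 | 0.54 |
| 0.8, 1.5 | 0.300 | √(1.16 × 1.5625) = 1.346 | 0.22 | 0.45 | 0.59 |
| 1, 2 | 0.500 | √(1.25 × 2) = 1.581 | 0.32 | 0.51 | 0.63 |

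With 35% men (or 65%; pq = 0.2275) the r_w = 0 column becomes 0.10, 0.21 and 0.30, so the sex mix matters little.

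**Impedance.** If the gap between the two cut-offs (7 − 5.7 = 1.3 kg/m²) stands in for the sex difference, and a within-sex SD of 1.0 kg/m² is assumed, dy = 1.3. For dx = 0.5 and 1.0, r_w = 0 shows as 0.13 and 0.24, and r_w = 0.30 as 0.38 and 0.47.

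**Gait speed.** With dy = 0.2 and dx from 0.5 to 1, r_w = 0 shows as 0.02 to 0.04 and r_w = 0.30 as 0.31. With dy = 0, pooling lowers the coefficient: 0.30/√1.0625 = 0.29 and 0.30/√1.25 = 0.27.

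**Tests when r_w = 0.** By Fisher's z with n = 118 and two-sided 5% (the plan does not state sidedness), the pooled coefficient is significant in about 21%, 68% and 94% of studies for the three rows of the table. In 4,000 simulated studies per setting with 59 men and 59 women:

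- pooled Pearson rejected in 31% (dx 0.5, dy 1.3), 79% (1, 1.3) and 96% (1, 2);
- Spearman was within 1 percentage point of Pearson;
- the sex-adjusted partial correlation rejected in 4.5 to 5.3% over all settings run.

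**Cost of adjusting.** The smallest correlation detectable with 80% power at n = 118 moves from 0.255 unadjusted to 0.257 adjusted for sex. In 59 patients of one sex it is about 0.36.

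**The case against.** Several points on the other side are sound.

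- **A reader might infer that the study's validity claim is compromised.** The documents do not support that. Section 10.4 assigns validity to ROC areas, sensitivity, specificity and predictive values, and the correlations are a separate secondary objective. This point does not touch the primary accuracy result.
- **A reader might infer that sex alone would reproduce whatever is reported.** On the figures above, sex alone yields 0.11 to 0.32. It would not produce a pooled 0.37 to 0.51.
- **The rejection rates of 21 to 94% apply only if thickness is wholly unrelated to the comparator within each sex.** Section 1.5 takes the opposite view, that loss of thickness or area goes closely with loss of strength. On that premise the relevant effect is inflation of a real correlation, not a false discovery.
- **Upward bias is not general.** It needs a clear sex difference in both variables. Section 1.4 says gait reference values take sex into account but gives no size. Section 8.3.2 also collects cross-sectional area, echogenicity and pennation angle, and 10.5.1 does not say which measures are correlated. The working here covers thickness only.
- **The unadjusted coefficient is a legitimate quantity.** For two measures of muscle quantity, the difference between men and women is real variation in muscle, and the objective does not say whether the overall or the within-sex association is meant. This is a good reason to keep the pooled coefficient. It is not a reason to report it alone.
- **No bias has been shown from age or height.** Age-related muscle loss may be part of what the tool should detect, and the impedance indices are already scaled to height. A coefficient adjusted for all three as the sole headline is not justified.

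**Conclusion.** The point holds in limited form. Section 10.5.1 plans only unadjusted correlations in a mixed-sex cohort, while the protocol treats each comparator as depending on sex. For handgrip and impedance the pooled coefficient could partly reflect sex. For a within-sex correlation of 0.30, the inflation is 0.07 to 0.21 (0.37 − 0.30 to 0.51 − 0.30). For gait speed the effect may be negligible or slightly reversed.

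These sizes rest on assumed sex differences of 0.5 to 1 SD in thickness and 1 to 2 SD in the comparator, equal sexes and n = 118. The documents can neither confirm nor exclude them. The consequence is confined to a supporting secondary objective. The change is still worth making before analysis: it uses data already collected, and it prevents a choice between coefficients after the results are seen.

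**What to change.** In section 10.5.1:

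1. Pre-specify the sex-adjusted partial correlation (Pearson or rank, by the rule already in the plan) with its 95% CI for each comparator.
2. Report it beside the planned pooled coefficient and the coefficients for men and for women.
3. State that any conclusion that ultrasound tracks strength or muscle mass rests on the sex-adjusted value.
4. If wanted, add adjustment for age and height as a sensitivity analysis only.

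The cost is a few lines of text and about one degree of freedom (115 instead of 116 at n = 118). The sex-specific estimates will be less precise and should be read as descriptive. No new data are needed and N does not change.

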4.2 Secondary endpoint

Secondary endpoints will be:

- Correlation measurements of muscle ultrasound with:
 - Bioelectrical impedance;
 - Handgrip;
 - Walking speed.
- Comparison of the diagnostic accuracy in undernutrition of muscle ultrasound with those of :
 - Bioelectrical impedance;
 - Handgrip;
 - Walking speed.
- Measure of association of muscle ultrasound measurements with patient morbidity and mortality:
 - Length of hospitalization (days);
 - Mortality: proportion and date of occurrence of death among patients included during hospitalization;
 - Autonomy at discharge: Activities Daily Living (ADL) score, **Appendix 1**.

5 Eligibility Criteria

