7.2.4 Measurements of muscle function

Measurement of grip strength ("Handgrip")

The gripping force is evaluated with the Jamar® hydraulic force gauge by the caregiver.

The patient is in a sitting position, on a chair with a backrest, with his feet on the floor. The device is placed in the patient's hand. The patient is instructed to squeeze the dynamometer as hard as possible.

The measurement is made on the dominant side of the patient. The homolateral shoulder is in adduction (elbow to body), without extension or flexion and in neutral rotation. The elbow is flexed to 90° and in neutral prono-supination. The wrist is in neutral position. Three trials will be performed, and

the best value (in Kg) of the different tests is retained (see measurement procedure in [Appendix 2](#)).

Measurement of the walking speed ("Gait speed")

Walking speed (m/s) is measured on a 4-meter course, in a corridor, by the EAPA or the physiotherapist. The course is marked out on the ground. The course is marked out with markings on the ground and there are also 1-metre run-up and run-down zones. The patient is instructed to walk the course at a normal speed and not to complete the distance as quickly as possible. The course is completed 3 times and the best time (in seconds) is recorded (see procedure in [Appendix 3](#)).

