8.2 Bioelectrical impedanceometry

Bioelectrical impedanceometry is performed in the patient's room using the Z-Metrix impedance meter from Bioparhom. The test is performed when the patient is admitted to the ward.

The patient is positioned in dorsal decubitus, inclined at 30 degrees. The patient must rest for at least 15 minutes before the measurement. Four electrodes will be placed:

- On the flat of the back of the hand;
- At the wrist, at the level of the head of the ulna, in the intertendinous hollow;
- At the ankle, above the external malleolus;
- Above the previous electrode, spaced about 4 fingerbreadths apart.

This non-invasive test quantifies muscle, lean and fat mass as well as bone and water mass. The values are expressed in kilograms and as a percentage of body weight (see measurement procedure in [Appendix 5](#)).

The following clues will be collected:

- Muscle mass index (in kg/m^2);
- The non-fat mass index (in kg/m).²

The operator performing the bioelectrical impedanceometry will be blind to the results of other examinations performed on the patient.

The threshold used will be 7 Kg/m^2 for men and 5.7 Kg/m^2 for women, as recommended (Cederholm T et al. Clin Nutr 2019)

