8.3.2 Realization of the measurement

A linear probe will be used for measurements of thickness, echogenicity and cross-sectional area of the rectus femoris and vastus intermedius, according to the procedure described in **Appendix**

6. The patient is placed in the supine position (as strict as possible), with the lower limbs in extension and in a neutral position of rotation. The probe is placed on the anterior aspect of the thigh, 2/3 of the distance between the anterior superior iliac spine and the upper edge of the patella, in line with the femur.

In order to evaluate inter and intra-examiner reproducibility, the tests will be performed by two different operators and twice by the same operator, i.e. 3 identical examinations in total. In the transverse plane, the distance between the upper and lower fascia of the muscle body will be measured, directly on a frozen image. The thickness of the rectus femoris and the vastus intermedius will be measured on the right side at rest, without patient participation. The average of 3 measurements per muscle is retained to improve the reliability of the measurement.

The cross-sectional area (CSA) will also be measured. Also in the transverse plane, the cross-sectional area of the rectus femoris and the vastus intermedius will be measured using the "caliper" function to trace the limits of the muscle and measure its surface. On the same frozen image, echogenicity will be measured using the Image J software® using the entire muscle surface.

The pennation angle of the rectus femoris will also be measured in a longitudinal plane. The

SAURON
operator performing the ultrasound will be blinded to the results of the other examinations
performed on the patient.

Version 5 of 22/09/2022

9 Conduct of the research

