16.6 Appendix 6: Protocol for performing muscle ultrasound

A linear probe will be used for the measurements. A set of predefined settings of the gain and depth parameters will be used for all measurements.

Patient positioning

The patient is installed in dorsal decubitus (as strict as possible), with the lower limbs in extension and neutral position of rotation.

Placement of the probe

The probe is placed in contact with the skin via an ultrasound gel. The pressure exerted with the probe is perpendicular to the plane of the bed, in line with the femur and must be as low as possible to obtain a representative image of the muscle. Excessive pressure will cause deformation of the subcutaneous tissues and therefore of the muscle. There are two ways of orienting the probe: in the transverse or sagittal plane.

Measurements on the quadriceps

[figure not shown]

Figure 1

The probe is placed on the anterior aspect of the thigh, 2/3 of the way from the anterior superior iliac spine to the upper edge of the patella, plumb with the femur (**Figure 1**) (39). The muscle chiefs studied were the rectus femoris and the vastus intermedius.

[figure not shown]

Figure 2

Muscle thickness

In the transverse plane, measurement of the distance between the upper and lower fascias of the muscle body (Figure 2). It is measured directly on a frozen image. The thickness of the rectus femoris (DF) and the vastus intermedius (VI) will be measured on the right. The average of 3 measurements will be taken.

[figure not shown]

Figure 3

Cross-Sectional Area (CSA):

Still in the transverse plane, measure the cross-sectional area of the rectus femoris using the caliper to delineate the boundaries of the rectus femoris (Figure 3).

Pennation angle

Place the probe along the axis of the rectus femoris muscle. The angulation of the muscle fibers in relation to the underlying fascia becomes visible (pennation of the fibers (Figure 4)). Record the image. The angle between a muscle fiber and the underlying fascia will be measured only on the rectus femoris, on the Image J software.

[figure not shown]

Figure 4

Echogenicity

Save the image used to measure the thickness and the sectional area. In the Image J software, delineate the entire muscle sectional area and analyze the variations in gray levels. The software provides a histogram with an overall gray level value ranging from 0 to 255 - 0 corresponding to black and 255 to white (28).

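### The only Bland-Altman analysis sits under comparisons that share no unit, while the repeated scans that could use it get an ICC of unstated form

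*Combined protocol and SAP*

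**What the plan says.** Bland-Altman is mentioned once, in section 10.5.1, the secondary analysis of ultrasound against the standard muscle-function measures: "The agreement between quantitative variables will be evaluated using the Bland-Altman method and that between qualitative variables using the Kappa coefficient". The sentence names no pair of variables. The matching endpoint in section 4.2, introduced as "Correlation measurements of muscle ultrasound with", lists bioelectrical impedance, handgrip and walking speed. Section 10.5.1 also plans Pearson or Spearman coefficients.

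For the repeated scans, section 8.3.2 says: "In order to evaluate inter and intra-examiner reproducibility, the tests will be performed by two different operators and twice by the same operator". That makes three identical examinations per patient. Their analysis, in section 10.4, is one sentence: "Inter- and intra-examiner reliability will be assessed by calculating intra-class correlation coefficients". The form of the ICC is not given. Section 10.2 adds 95% confidence intervals for every estimate and paired tests where needed. It mentions no bias, limits of agreement or standard error of measurement (SEM).

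**The concern.** Bland-Altman works on the difference between two measurements of the same quantity in the same unit. Under the heading of 10.5.1, no ultrasound measure has a comparator in its own unit. An analyst who follows the text would report a bias and limits of agreement that cannot be interpreted.

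The scans by two operators, one of whom scans twice, are data for which the method is suited. Reliability is half of the main objective (section 3.1), and the ICC calculation sets the sample size (section 10.1). The study also intends to propose ultrasound thresholds (sections 2 and 11). To judge a threshold, a reader needs the measurement error in the unit of that threshold and needs to know whether operators differ systematically. An ICC on its own states neither. It also rises with the spread of the patients, and this sample mixes diabetes-obesity, pneumology, oncology and gastro-nutrition.

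**Working it through.** **1. Unit check**

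| Measure | Scale | Source |
|---|---|---|
| Ultrasound thickness | length: "the distance between the upper and lower fascia of the muscle body will be measured" | 8.3.2 |
| Ultrasound cross-sectional area | area | 8.3.2, Appendix 6 |
| Pennation angle | angle | 8.3.2, Appendix 6 |
| Echogenicity | "overall gray level value ranging from 0 to 255" | Appendix 6 |
| Impedance index | kg/m² | 8.2, 10.4 |
| Handgrip | kg: "the best value (in Kg) of the different tests is retained" | 7.2.4 |
| Walking speed | m/s | 7.2.4, Appendix 3 |

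No ultrasound row has the unit of any comparator row. No calibration equation, standardisation or conversion is planned.

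**2. What the output would look like.** The values here are assumed for illustration: thickness mean 15 mm, SD 4; muscle index mean 6.5 kg/m², SD 1; correlation 0.6.

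- In mm: bias = 15 - 6.5 = +8.5. SD of differences = √(16 + 1 - 2×0.6×4×1) = √12.2 = 3.49. Limits = 8.5 ± 1.96×3.49, about 1.7 to 15.3.
- In cm: bias = 1.5 - 6.5 = -5.0. SD of differences = √(0.16 + 1 - 2×0.6×0.4×1) = √0.68 = 0.82. Limits about -6.6 to -3.4.
- The correlation is 0.6 in both cases.

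The bias changes sign with the choice of unit. The correlation does not move.

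**3. The plan's own reliability figure.** Section 10.1 gives ρ1 = 0.80, ρ0 = 0.70, k = 2, α = 0.05, power 80% and N = 118. With the Walter-Eliasziw-Donner approximation:

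- C0 = [1 + 2×0.7/0.3] / [1 + 2×0.8/0.2] = 5.667/9 = 0.630, and (ln C0)² = 0.214.
- n = 1 + 2(1.645 + 0.842)²×2 / [0.214×(2 - 1)] = 116.6, rounded up to 117.

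This agrees with 118 to within rounding, for one-sided α. The plan does not state sidedness; two-sided α would give 148. Nothing below depends on this.

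**4. What those ICC values mean as measurement error.** Assume no operator bias and express everything in units of the total SD. Then SEM = √(1 - ICC), SD of differences = √2 × SEM, and limits = ±1.96 × SD of differences.

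| ICC | SEM | 95% limits of agreement |
|---|---|---|
| 0.80 (expected) | 0.447 | ±1.24 |
| 0.70 (minimum acceptable) | 0.548 | ±1.52 |

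**5. Precision with 118 pairs.** The 95% CI half-width of each limit is about 1.96 × √(3/118) = 0.31 SD of the differences. In total-SD units that is about 0.20 at ICC 0.80 and 0.24 at ICC 0.70.

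**6. Why the ICC form matters.** Take patient variance 0.8 and error variance 0.2, and let one operator read higher by a constant b (in units of the offset-free total SD). With two operators the offset adds b²/2 to the denominator of an absolute-agreement ICC and nothing to a consistency ICC.

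| Offset b | Consistency ICC | Absolute-agreement ICC |
|---|---|---|
| 0 | 0.80 | 0.80 |
| 0.5 | 0.80 | 0.8/1.125 = 0.71 |
| 1 | 0.80 | 0.8/1.5 = 0.53 |

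**The case against.** The strongest reply is that the sentence in 10.5.1 is generic method text, arranged by type of variable, and assigns Bland-Altman to no pair. That is so. The link to impedance, handgrip and walking speed comes from the section heading and section 4.2. A reader might infer that the plan expressly orders ultrasound to be subtracted from each of these; the text does not go that far. What stands is that the sentence has no valid ultrasound pair under its heading, and that section 10.4 does not refer to it. If it was meant for the repeated scans, it needs to be moved there.

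Second, no endpoint depends on it. The endpoint is correlation, and valid methods for it are given in the same section. This is correct and limits the harm to an uninterpretable supplementary output.

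Third, an ICC is a legitimate reliability index and matches the basis of the sample size. An absolute-agreement form would penalise an operator offset, and the SEM can be derived from the ICC and the SD. All of this is fair, so it would be too strong to say that the plan has no means of detecting disagreement between examiners. But the form is unstated, and under a consistency form an offset would go unseen. Nor does an ICC of either form show the direction of an offset or its size in thickness units.

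**Conclusion.** The point holds in a limited form. As placed, the Bland-Altman analysis gives results that depend on an arbitrary choice of unit. The reliability analysis lacks operator bias and measurement error in thickness units, and does not say which ICC is meant. At the plan's own expected ICC of 0.80, two scans of the same patient could differ by up to about 1.24 total SDs in 95% of cases. At the acceptable minimum of 0.70 the figure is 1.52. These figures assume roughly normal differences, constant error and no operator bias. The mm and cm example uses assumed values and only shows the dependence on units.

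Two stronger conclusions might be drawn, and the documents support neither. One is that the correlation objective is compromised: Pearson and Spearman remain valid for it. The other is that Kappa in the same sentence is also misplaced, or should be confined to ultrasound against impedance. Kappa between any dichotomised tools is workable. It also serves the aim in section 11 of examining how different tools change the estimated prevalence.

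This is a minor correction to a secondary analysis, with a useful addition to the primary reliability analysis.

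**What to change.** - **Section 10.5.1:** delete Bland-Altman. Keep Pearson or Spearman for quantitative pairs and Kappa for agreement between dichotomised tools.
- **Section 10.4:** keep the ICC and state its form, with absolute agreement for the inter-examiner comparison. For rectus femoris thickness, add the mean difference (bias), the 95% limits of agreement with confidence intervals, and the SEM. Report these separately for the intra-examiner and inter-examiner pairs, and state which of the first operator's two scans enters the inter-examiner pair.

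The cost is a few sentences. The three examinations are already planned, so there are no new data, no added patient burden and no change to N = 118.
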